After the escalation in their treatment at baseline (Study Visit I) these patients will return for a second (24 weeks) study visit respectively and the set of evaluations shown in the table below - and in more detail in Appendices I, II and III - will take place. A window of +/- 2 weeks will be allowed in scheduling the study visits.

Visit II	
Evaluations	Mar/2012-Jan/2015
Cardiac PET-CT scan*	X
3D Echocardiogram	X RA &
CV Questionnaires	X
Joint examination	X
DEXA scan (body composition)	X
Phlebotomy	X
Anthropometry	X

\*including 3 transverse CT slices (mid-chest, L4-L5, mid-thigh) and low dose radiation chest CT

During PET-CT scans a low dose CT imaging of the chest is always obtained for attenuation correction as part of the usual PET-CT protocol. Although we will not need a repeat coronary artery calcium score at visit 2, low dose radiation CT imaging of the chest is always obtained for attenuation correction as part of the usual PET protocol. During this CT imaging acquisition 3 additional slices (CT cuts) will be again obtained (mid chest, lumbar, and mid thigh) to evaluate for change in visceral fat following treatment initiation.

The 3-dimensional Echocardiogram (3D Echo) will be performed to provide a measure of LV mass and will be performed in every study visit.

The 15 controls will also be asked to have a repeat set of evaluations 6 months (24 +/- 2 weeks) after their first evaluation without any therapeutic or other intervention in between the two visits. The inclusion of non-RA controls will provide important data on the normal variation of cardiac PET-CT and 3D Echo parameters over time. Further evaluations for the control participant visits are outlined in appendices I, II and III.

Every subject (RA patient or non RA control) will have a urine pregnancy test prior to tests involving radiation exposure (PET-CT scan and DEXA) and on the same day.

The screening and consent process of a patient to receive randomized escalation of treatment will be made at the time they are consented for the first study visit. It is possible that all 150 patients will qualify for randomization of their treatment but only the first 50 of those will be selected to return for study visit II. The rest of the patients will exit the study and will continue their regular care with escalation of their treatment by their treating rheumatologist outside the study.

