As already mentioned, the goal of this study is to investigate the "low LV mass phenotype" in patients with RA and its contributors in an attempt to elucidate the pathophysiology pathways that may connect RA with alterations in the myocardium and the evolution to heart failure. 3D-Echo will be used to measure the LV mass. Cardiac PET-CT imaging will be used to evaluate myocardial function (cardiac output, ejection fraction), microvasculature function (myocardial perfusion) and myocardial inflammation (F18-FDG uptake).

The research questions to be addressed with the study visit I are the following:

- i) Are anti-CCP antibodies or other RA-specific characteristics (e.g., disease duration, activity, severity) associated with lower LV mass (or other LV parameters of structure/function)?
- ii) What is the prevalence, the degree and correlates of microvascular dysfunction in RA? Is it associated with low LV mass or reduced global or regional contractility? Is it associated with systemic, articular and/or myocardial inflammation?
- iii) What are the prevalence, patterns, distribution and severity of inflammation as measured by F18-FDG uptake in myocardial PET imaging? Are intensity and/or distribution of F18-FDG uptake correlated with low LV mass or global or regional contractility? Does the severity/distribution of F18-FDG uptake correlate with levels of systemic and/or articular inflammation?

For the second aim of this study the goal is to evaluate the effect of TNF inhibitors on the myocardium. For the 50 patients undergoing randomization and the controls the questions to be addressed will be the following:

- i) Are global measures of LV structure (e.g., mass) or contractility (e.g., ejection fraction) affected (reduced or increased) by treatment with TNF antagonists? Is there a different effect compared to alternative therapy?
- ii) If microvascular dysfunction and/or inflammation are present before treatment, do they improve with treatment with TNF compared to alternative treatment? If parameters improve only with TNF inhibitor, this would suggest that TNF inhibitors exert a local anti-inflammatory effect on the myocardium mechanistically different compared to alternative treatment.
- iii) If treatment-induced improvements in microvascular dysfunction and/or inflammation (F18-FDG uptake) are

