Linear mixed effects (MIXED) regression models will be used to assess trends in LV structure and functional outcomes over time between the two visits for the patients who will undergo randomization reevaluation with PET-CT and 3D Echocardiogram, while controlling for potential confounders. The data will include PET-CT studies for 25 RA patients receiving TNF antagonists and 25 RA patients receiving alternative treatment, and PET-CT studies for 15 non-RA patients. The data are longitudinal since LV outcomes are measured for each person at 2 different time points. Since repeated measures tend to be correlated within a person, mixed models with both fixed and random effects will be used to adjust for this correlation. We will use unstructured correlation structure given that each visit will occur roughly around a fixed time since study visit I, and use robust standard error estimates to conduct statistical inferences. To study the TNF inhibitor effects on LV structure or functional outcomes, visit-specific indicators, RA status, TNF treatment status, and visit x TNF treatment interaction will form the bases for the mean model. The visit-specific indicators will capture the time trend of LV outcomes over the study period, the RA status will delineate the overall mean difference in LV outcomes between RA and non-RA, with the TNF treatment status indicator and its interaction with visit indicators capturing the baseline difference in LV outcomes between TNF treated and non-treated groups and the potential TNF treatment effect on LV outcome over time, respectively. Actual TNF inhibitor dosage could be used in place of TNF status indicator in the model if necessary, and other potential covariates could be added into the model for confounding adjustment. For example, inflammation markers could be added into the model to examine whether any TNF treatment effect is mediated through the change in systemic inflammation. Similar modeling approaches can be used to study all research questions of interest using the corresponding outcomes and their hypothesized predictors listed in those questions to be addressed. For any binary outcomes in this type of regression analysis, e.g. indicator of whether a LV outcome exceeding certain critical value, generalized linear mixed effects models (GLIMMIX) can be used to study the odds of such outcome as a function of the independent variables.

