We will obtain valuable information on LV structure/function outcomes for the cross-sectional visit, as well as for change in these outcomes over 6 months, for 3 groups of study participants, 25 RA patients treated with TNF-antagonist, 25 RA patients treated with triple treatment or alternative, and 15 non-RA participants with otherwise similar characteristics. For continuous outcomes we will obtain mean, standard deviations, and skewness (to inform us whether certain variables may need transformation before analyses so that sample size/power evaluation for future studies may need to be based on transformed data) for cross-sectional as well as the change over time measurements, and the correlations between two consecutive measurements over time. For binary variables we will obtain prevalence estimates and odds ratios as estimates of association between two repeated binary measures over time. Even accounting for a possible 15% drop out rate of participants, the correlation estimate will have precision ranged approximately between within +/- 0.33 for a correlation of 0.50 and within +/- 0.09 for a correlation of 0.90. For prevalence of binary outcomes, our estimate will be ranged approximately from within +/- 17.9% for a prevalence of 50% to +/-10.7% for a prevalence of 90%. To estimate the power of detecting a 24 week (6 month) change in an LV myocardial outcome within the TNF treated RA group, with a 2-sided alpha of 0.05 and N=22 (accounting for possible drop out), we calculated the minimal detectable change based on cross-sectional SDs and various values for within person correlation between outcome measures at subsequent visits based on data from previous studies performed by the same investigator group. For example with a conservative SD of 1.8 L/min for cardiac output (CO) and 4.2 mL/m^2 for stroke volume (SV) and the correlation between subsequent visits being 0.2 we will have 80% power to detect a 24 week (6 month) change of 1.47 l/min for CO or 3.42 ml/m^2 for SV or more in the TNF inhibitor treated RA group. Similarly in order to estimate power for comparing changes between the TNF inhibitor treated group, the triple therapy treated group and the normal control group we based our calculations with comparing the changes between those groups with one way ANOVA assuming a 15% drop out and a 2-sided alpha of 0.05. We will have 80% power to detect any set of 3 group differences/changes if the SD of the changes is 0.444 or greater. We will have 80% power to detect a difference through the 3 group-one-way-ANOVA if the mean 24 week (6 month) change in SV for the TNF inhibitor group is 5.2ml/m^2 or higher while the mean change for the other two groups is 0. To provide a context regarding the number used above as an expected change in SV we would like to mention here that in our pilot data we observed a change in SV of 12.5mL/m^2 or higher with TNF inhibitor treatment in patients with RA.

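### Aim 2 reads the TNF effect from change with a free baseline difference, which wastes precision in a 25-per-arm comparison; as written, its comparator also mixes triple therapy with non-RA controls

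*Combined protocol and SAP*

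**What the plan says.** Section 2a (Study Design) asks of TNF inhibitor treatment: "Is there a different effect compared to alternative therapy". The analysis offered is a linear mixed model over two visits with unstructured correlation and robust standard errors, in 25 TNF patients, 25 patients on alternative treatment and 15 non-RA controls. Its fixed effects are listed: "visit-specific indicators, RA status, TNF treatment status, and visit x TNF treatment interaction will form the bases for the mean model". The text then gives the roles of the terms: "the TNF treatment status indicator and its interaction with visit indicators capturing the baseline difference in LV outcomes between TNF treated and non-treated groups". The interaction is to carry the treatment effect over time.

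The Visit I value of the outcome is not named as a covariate, and the two randomised arms are not given a common baseline mean. The only opening is that "other potential covariates could be added into the model for confounding adjustment".

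Section 2b (Sample size and power calculations) also works on change: "we based our calculations with comparing the changes between those groups with one way ANOVA assuming a 15% drop out". Its stroke volume (SV) example has a TNF change of 5.2 mL/m² "while the mean change for the other two groups is 0". The within-arm calculations used "various values for within person correlation between outcome measures at subsequent visits"; the examples give r=0.2 for cardiac output (CO) and SV, and r=0.35 for LV mass.

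**The concern.** Randomisation makes the expected Visit I means of the two RA arms equal. A free TNF main effect discards that knowledge and forces the baseline slope to 1. When visits correlate weakly, as in the plan's own examples, subtracting the whole baseline value adds noise. The arms are small: 25 each, or about 21 after 15% dropout (25 x 0.85 = 21.25). The RA-only test remains valid; precision is what is lost.

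The same sentence raises a second, separate issue. Without a visit x RA term, triple therapy patients and non-RA controls must share one time trend. The visit x TNF term then compares TNF with a pool of the two, and the pool is not the randomised comparator. Section 2a gives the controls another purpose: "The inclusion of non-RA controls will provide important data on the normal variation of cardiac PET-CT and 3D Echo parameters over time". Baseline adjustment alone does not cure this.

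**Working it through.** **Inputs.** From section 2b: LV mass SD 27 g in RA and 40 g in normal people; SV SD 4.2 mL/m²; r=0.2 (CO, SV) and 0.35 (LV mass); 15% dropout. r=0.9 is the upper value in the plan's precision statement, not a power input; r=0.5 is the lower value there. Tests are two-sided at 0.05. No Visit II SD under treatment is given, so SD 27 to 40 g in both arms is my assumption, used as a range.

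**1. The plan's figure.** Section 2b claims over 85% power for a 27 g difference between arms. With SD 27 g at both visits and r=0.35, the variance of change is 2(1−0.35)×27² = 947.7. At 25 per arm the standard error is √(2×947.7/25) = 8.71 g, and noncentral-t power is 86.0%. The claim therefore reproduces as an unadjusted comparison of changes, before dropout.

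**2. Variance of TNF versus triple therapy, RA patients only, complete data.** Per patient:
- change: s1² + s2² − 2r·s1·s2
- baseline-adjusted: s2²(1−r²)

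With equal SDs the ratio is (1−r²)/(2(1−r)) = (1+r)/2. Estimating the slope multiplies the adjusted variance by 1 + 1/(N−4), which is 1 + 1/38 at N=42.

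| r | ratio | cut | cut after slope cost, 21 per arm |
|---|---|---|---|
| 0.2 | 0.600 | 40% | 38% |
| 0.35 | 0.675 | 32.5% | 31% |
| 0.5 | 0.750 | 25% | 23% |
| 0.9 | 0.950 | 5% | 2.5% |

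If 25 per arm attend Visit I and 4 per arm miss Visit II, the free-baseline model already recovers a little. With the covariance taken as known, the cuts become 36%, 29%, 22% and 4%.

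For LV mass with SD 27 to 40 g in both arms at r=0.35: change 729 + 1600 − 2×0.35×27×40 = 1573; adjusted 1600×(1−0.1225) = 1404; ratio 0.893, a cut of 11%. At other r the cut is 19% (0.2), 4% (0.5) and nil (0.7). At r=0.7 the slope r·s2/s1 is 1.04, so change is already near optimal and the slope cost makes adjustment 2.5% worse.

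**3. Power and detectable difference, slope cost included.**

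| Case | change | adjusted |
|---|---|---|
| Power for 27 g, SD 27, r=0.35, 25 per arm | 86.0% | 95.5% |
| Same, 21 per arm | 79.2% | 91.5% |
| Power for 27 g, SD 27 to 40, r=0.35, 21 per arm | 58% | 61% |
| LV mass at 80% power, SD 27, r=0.35, 21 per arm | 27.3 g | 22.7 g |
| LV mass at 80% power, SD 27 to 40, r=0.35, 21 per arm | 35.1 g | 33.7 g |
| SV at 80% power, r=0.2, 21 per arm | 4.71 mL/m² | 3.70 mL/m² |
| SV at 80% power, r=0.9, 21 per arm | 1.66 mL/m² | 1.64 mL/m² |

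**4. The comparator in the model as written.** A generalised least squares fit of the listed terms at 25/25/15 gives visit x TNF = (TNF change) − 0.625 (triple therapy change) − 0.375 (control change), since 25/40 = 0.625 and 15/40 = 0.375. This equals the wanted contrast plus 0.375 × (triple therapy change − control change), or 3.75 g for each 10 g by which those two groups differ. A simulation of 20,000 trials with changes of 27, 10 and 0 g (true contrast 17 g) gave a mean of 20.75 g from this model and 16.98 g from either RA-only analysis.

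**5. Net effect of correcting both.** Relative to the pooled model, an RA-only model with a common baseline has variance ratios (equal SDs) of 0.0768/0.1040 = 0.74 (r=0.2), 0.0702/0.0845 = 0.83 (0.35), 0.0600/0.0650 = 0.92 (0.5) and 0.0152/0.0130 = 1.17 (0.9). Break-even is where (1+r)/2 = (1/25+1/40)/(2/25) = 0.8125, so r=0.625. With SD 27 to 40 g at r=0.35 the ratio is 112.3/102.2 = 1.10.

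**The case against.** The strongest reply is that a free-baseline longitudinal model is a recognised, valid analysis, so the first point is one of efficiency. That stands. The gain may also not matter for SV: at 21 per arm and r=0.2, the unadjusted two-arm comparison has 87% power for the plan's 5.2 mL/m² and over 99.9% for its pilot change of 12.5. That stands too; LV mass is where the gain matters, because unadjusted power falls below 80% after dropout if SDs are equal.

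The 40 g is the SD in normal people, and the plan posits a move to 147 g only for TNF. If only the TNF arm reaches 40 g, the cut at r=0.35 is 18.5% (total variance 2520.7 to 2054.0), so 11% is the cautious figure.

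A common baseline mean presumes that Visit I measurements precede treatment, which section 2a does not state; it allows PET-CT up to a week from Visit I. This is worth stating in the plan, but it does not favour change scores. An early effect at Visit I is subtracted in full by change and only in proportion to the slope by adjustment, so it distorts the adjusted estimate less whenever the slope is below 1.

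Finally, the listed terms are called the basis of the model, so a visit x RA term might have been intended. That is possible, but the text does not include one, and the optional covariates are offered for confounding.

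**Conclusion.** The concern holds. For the randomised TNF versus triple therapy contrast, the change-based estimate is valid but gives away precision: 40% to 5% of variance for r from 0.2 to 0.9 with equal SDs, and 11% for LV mass if the SD rises to 40 g in both arms at r=0.35. These are complete-data values before the slope cost of roughly 1.5 to 2.5 percentage points. The gain vanishes where r·s2/s1 is near 1.

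The comparator problem is distinct and is one of bias: 0.375 times any difference in change between triple therapy and controls. It is zero only if those groups change alike, as the plan's SV example assumes. If pooling was intended, correcting it can raise variance (by 17% at r=0.9, or 10% for LV mass with SD 27 to 40 g at r=0.35). That is the price of the contrast the research question asks for.

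**What to change.** For the two randomised arms, specify a mixed model with a common Visit I mean, that is, without the TNF main effect. Either restrict it to RA patients or add a visit x RA term, so that visit x TNF means TNF versus triple therapy. The two versions have the same variance for this contrast, and both keep Visit I data from patients who miss Visit II. ANCOVA of the Visit II value on arm and the Visit I value of the same outcome is an alternative. State that Visit I outcomes are measured before the randomised treatment starts, if that is so.

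Restate between-arm power and detectable differences on this basis over a range of r (for example 0.2 to 0.9), and for LV mass also with SDs of 27 and 40 g.

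The cost is a sentence or two of analysis text, a re-run of the power figures and one degree of freedom. The Visit I values are already collected. Controls would no longer lend precision to the comparator.

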Standard of care entails that patients who undergo escalation of their treatment need to be evaluated every 6-8 weeks to evaluate response to treatment, the need for further treatment escalation, and toxicity monitoring. Thus in between Study Visits I and II patients will return every 6-8 weeks for safety visits which will mirror standard of care management and which will be focused on toxicity monitoring as it would happen even if the patients did not participate in the study. An exit safety visit will occur 6-8 weeks after visit II. The incorporation of safety visits in the study and the related procedures/tests are shown in Appendices I and II.

It is possible that patients randomized to receive either the triple therapy or treatment with a TNF inhibitor and methotrexate may not respond to treatment. Disease activity will be evaluated using the Clinical Disease Activity Index (CDAI) score at the time of every safety and study visit and treatment will be modified until they reach the state of low disease activity or remission as defined by a CDAI score of less than or equal to 10. CDAI score takes into account the number of swollen and tender joints and the evaluation (using a Visual Analog Scale) of disease activity by both the patient and the physician. CDAI is an extensively validated disease activity tool.

[figure not shown]
The treatment algorithm followed in this study is described below. A study flow chart describing the algorithm is provided in appendix XXI.

i. Randomization to the non TNF inhibitor arm: Patients on triple therapy will be started on 1 gram of sulfasalazine (SSZ) twice daily along with weight adjusted daily Hydroxychloroquine (Plaquenil). Methotrexate treatment will be continued. It takes approximately 6 weeks before an effect of this therapeutic regimen is experienced. In the first safety visit (which will happen approximately 8 weeks after the first study visit) the need to increase the SSZ to 3 grams daily will be evaluated based on whether the patient has reached low disease activity status or remission. In the subsequent safety visit (safety Visit 2) which will occur 8 week after Safety Visit 1, if disease activity remains moderate or high, SSZ and Hydroxychloroquine will be stopped and patients will be switched to Leflunomide (Arava) 10 mg plus methotrexate.

Patients will then return at 24 weeks for their second Study Visit (Study Visit 2) for completion of the study and further management as per standard of care.

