An additional Safety Visit (Safety Visit 3) will take place at 32 weeks and will serve as an exit safety visit.

ii. Randomization to the TNF inhibitor arm: For patients randomized to receive treatment with a TNF inhibitor, disease activity will also be evaluated at the time of every visit. The effect of TNF inhibitors on arthritis activity may be observed as early as in 2 weeks but sometimes may take up to 14 weeks (approx. 3 months). At the time of the first safety visit tolerability and safety will be evaluated. At the time of Safety Visit II if CDAI is still >10 (indicative of moderate disease activity) an increase in the dose or frequency of the TNF inhibitor (in the case of agents such as infliximab or adalimumab where escalation of dosage is an option) or a switch to treatment to an alternative TNF

inhibitor will take place.

Patients will then return at 24 weeks for their Second Study Visit (Study Visit 2) for completion of the study and further management as per standard of care.

An additional Safety Visit (Safety Visit 3) will take place at 32 weeks and will serve as an exit safety visit.

The treatment algorithm described above is similar to the care patients would receive even if they did not participate in the study. The only difference is that patients will be randomized to receive one of the two standard of care treatments. The need for prednisone to temporarily control disease activity will be decided by the investigators according to usual standards of care.

As already mentioned decisions to escalate treatment will be based on CDAI score which is a composite disease activity score consisting of counts of swollen and tender joint counts and evaluation of disease activity by both the patient and the physician using a visual analog scale. The joint counts will be performed by a blinded trained joint assessor. Either a faculty member or a senior rheumatology fellow, also not aware of the patient treatment will perform the joint examinations and the assessment of disease activity. The same joint assessor will perform the joint counts for a given patient throughout the study. Every time CDAI is  $>10$ , then a change in the treatment according to the algorithm described above will be mandated to ensure patients' well being.

[figure not shown]

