observed with TNF inhibitor treatment and not with alternative treatment, do they correlate with (or mediate) global (or regional) changes in LV structure or function? If so, this would suggest a causal relationship between regional myocardial vasculopathy and/or inflammation with LV dysfunction.

iv) Do treatment-induced improvements in systemic inflammation (e.g., CRP) and RA disease activity correlate with changes in myocardial microvascular perfusion and/or inflammation? If so, this would suggest a relationship between systemic and myocardial inflammation.

In preliminary exploratory data analyses, summary statistics for the continuous and categorical variables will be calculated, including means, standard deviations, quartiles and ranges, and for the categorical variables, counts and percentages. In initial analyses, statistical comparison of continuous variables will be conducted using the t-test or nonparametric method, as appropriate. The comparisons of the prevalence of categorical CV risk factors will be conducted using the Chi-square test or the Fisher's exact test, as appropriate. All comparisons will be conducted at the  $\alpha=0.05$  level of significance using two-tailed tests, unless otherwise noted. To account for the potential for multiple comparisons artifact: a) First, significance testing will be based on a priori hypotheses and not spurious significant p-values; b) Second, if multiple comparisons are undertaken, adjustments in the threshold for statistical significance will be made as necessary. If multiple and collinear variables are detected, appropriate techniques will be utilized to minimize the impact of collinearity on the statistical efficiency of the derived parameter estimates.

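### The plan lets received TNF-inhibitor dose replace the treatment indicator, although dose rises only after poor response; used that way, the model no longer estimates the randomised contrast

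*Combined protocol and SAP*

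**What the plan says.** All places are in the combined protocol and SAP.

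- **Base model (section 2a, mixed-model paragraph).** "visit-specific indicators, RA status, TNF treatment status, and visit x TNF treatment interaction will form the bases for the mean model". The interaction carries the TNF effect over time.
- **Permitted substitute (same paragraph).** "Actual TNF inhibitor dosage could be used in place of TNF status indicator in the model if necessary". The plan gives no criterion for necessity, no definition of dosage (last, average or cumulative) and no statement that the status model stays primary. The same sentence goes on, in a separate clause, to allow covariates for confounding adjustment.
- **What changes TNF dose (section 2a, algorithm ii).** "At the time of Safety Visit II if CDAI is still >10 (indicative of moderate disease activity) an increase in the dose or frequency". Escalation is confined to certain products; for the rest, the patient moves to a different TNF inhibitor. More generally, when CDAI exceeds 10, "then a change in the treatment according to the algorithm described above will be mandated to ensure patients' well being". I found no other stated reason for raising TNF dose.
- **Comparator arm (section 2a, algorithm i).** If activity stays moderate or high at the second safety visit, "SSZ and Hydroxychloroquine will be stopped and patients will be switched to Leflunomide (Arava) 10 mg plus methotrexate". TNF dose remains zero whatever the response.
- **Agents (section 4).** Five TNF inhibitors are listed, with no conversion between their doses.

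**The concern.** Randomisation protects the comparison of the arms. It does not protect a comparison by dose received, because dose here is partly a consequence of how the patient did after randomisation. Within the TNF arm, a raised dose marks a patient whose arthritis did not settle. The same non-response in the comparator arm leaves the dose variable at zero. Non-response therefore moves the regressor in one arm only, and randomisation cannot balance that.

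Two separate problems follow if dose replaces the indicator:

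1. **Mis-scaling.** A slope per dose unit assumes that the effect is proportional to dose, over units that are not comparable across agents. If the effect does not follow that scale, power is lost even when response and cardiac outcome are unrelated.
2. **Confounding by response.** If non-responders also have a different LV change, the dose slope absorbs that difference. The study treats such a link as plausible. Section 1 hypothesises that inflammation may drive heart failure in RA, and section 2a asks: "Do treatment-induced improvements in systemic inflammation (e.g., CRP) and RA disease activity correlate with changes in myocardial microvascular perfusion and/or inflammation". That question concerns perfusion and myocardial inflammation; for LV mass the link is a further step. No size is given for either.

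At stake is the only randomised comparison in the study, with 25 patients per arm.

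**Working it through.** **1. The plan's own figure.** Section 2b gives an RA LV mass SD of 27 g, a within-person correlation of 0.35 (stated for the within-group calculation and carried over here) and a 27 g difference between arms.

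- SD of change = 27 × √(2 × (1 − 0.35)) = 27 × √1.3 = 30.8 g.
- With 25 per arm, SE = 30.8 × √(2/25) = 8.7 g, and 27/8.7 = 3.10.
- Two-sided power at 0.05 is 87.3% (normal) or 86.0% (t). The stated figure of more than 85% is reproduced.
- With 15% dropout, 25 × 0.85 = 21.25, so 21 per arm. The t-based power is then 79.2%.

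**2. Inputs the documents do not give (assumptions).**

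- Share of the TNF arm escalated: f = 0.4.
- Relative dose after escalation: 2, as a modelling unit only.
- Gap in LV change between non-responders and responders: g = 0, 0.5 or 1.0 SD of change, the same in both arms, with total SD held at 30.8 g.
- True TNF effect: the same for every TNF patient, whatever the dose.
- The 15 non-RA controls are left out. With two visits and complete data, the visit by arm term for the randomised patients is a difference in mean change.

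**3. Two readings of actual dosage.** Section 2a puts the first safety visit at about week 8, the second 8 weeks later (week 16), and the outcome at week 24.

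- Last dose: m = 2.
- Dose averaged over follow-up: m = (16 × 1 + 8 × 2)/24 = 1.33.

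**4. Large-sample result.** Code dose D as 0 in the comparator arm, 1 in TNF patients not escalated, and m in those escalated. With 1:1 allocation and mean TNF-arm dose d = 1 + (m − 1)f:

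- Var(D) = ½(1 − f + m²f) − (d/2)².
- Slope × d, from the true effect: effect × (d²/4)/Var(D).
- Slope × d, from the response link: −g × ½(m − 1)f(1 − f) × d/Var(D).

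| | m = 1.33 | m = 2 |
|---|---|---|
| d | 1.133 | 1.4 |
| Var(D) | 0.334 | 0.61 |
| Share of true effect kept, g = 0 | 0.96 | 0.80 |
| Bias for g = 1 SD | −0.136 SD = −4.2 g | −0.275 SD = −8.5 g |

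The bias is zero if g = 0. For a true 27 g effect at g = 1, the estimate is about 0.96 × 27 − 4.2 = 21.7 g (averaged dose) or 0.80 × 27 − 8.5 = 13.1 g (last dose).

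**5. Simulation.** 21 per arm, two-sided 0.05, change regressed on arm or on dose.

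| Regressor | Response link | Type I error | Power for 27 g |
|---|---|---|---|
| Randomised arm | any | 5% | about 79% |
| Dose averaged over 24 weeks | g = 0.5 to 1.0 | about 5-7% | about 61-70% |
| Last dose (0/1/2) | g = 0.5 to 1.0 | about 7-16% | about 29-49% |
| Dose, either coding | none | 5% | about 69-77% |

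**6. Sensitivity.** With 25 per arm, 25% or 50% non-responders all escalated, last dose coded 1.5 or 2, and a correlation of 0.3 to 0.5 between response and LV change, type I error is 0.059-0.129 and power 44-74%. The arm indicator gives about 0.05 and 85-86%. With 21 per arm, 20% escalated and averaged dose, type I error is 5.1-6.5% and power 66-73%.

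**The case against.** The best reply is that the plan's model is sound. Section 2a makes TNF status and its interaction with visit the basis of the mean model, and dose appears only as a possibility among other extensions. Under the algorithm, TNF-arm patients who change agent receive another TNF inhibitor and comparator patients go to leflunomide. Status and assigned arm therefore agree for anyone who follows the protocol. This stands. A reader might infer that the planned treatment-effect test is itself confounded, or invalid under the null. The documents do not support that, because the problem arises only if the swap is made.

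Three further points stand in part:

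- **Link to outcome.** Bias requires joint response to be related to LV change. The protocol raises such a link but does not quantify it. Without it, type I error stays at 5% and the cost is power alone.
- **Size.** The worst figures need last-dose coding, which treats 8 weeks of raised dose as if it covered all 24. Not every non-responder would be escalated either, since some agents call for a switch. Part of the power loss is mis-scaling: with last-dose coding and no response link, power is already about 69%.
- **Usefulness.** A dose analysis can be informative. That supports keeping one as a secondary description, but not letting it replace the randomised comparison.

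That the swap is optional does not remove the point. With no stated trigger, the choice could be made after the results are seen, which sits badly with the section 2a commitment to test prespecified hypotheses.

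**Conclusion.** The point holds as a fault in a permitted alternative, not in the base model. If received dose replaces the indicator, the treatment-effect estimate is no longer the randomised contrast.

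- **Without a response link:** type I error stays at 5%. Power for 27 g is about 69-77% instead of 79%, given an effect that does not scale with dose.
- **With a link of 0.5 to 1.0 SD:** about 5-7% type I error and 61-70% power with averaged dose, or about 7-16% and 29-49% with last dose. The bias is against TNF inhibitors when non-responders have the worse LV change, and would reverse if they had the better one.

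A reader might take the last-dose figures as the expected size, or the direction as certain. Neither follows. The escalated share, the dose ratio, the response gap and the dose definition are all assumptions, and the documents fix none of them. The principle is firm; the size is not. The wording should be corrected, because doing so is almost free and protects the main comparison in aim 2.

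**What to change.** In the mixed-model paragraph of section 2a:

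1. Delete only the clause "Actual TNF inhibitor dosage could be used in place of TNF status indicator in the model if necessary". Keep the rest of that sentence, on covariates for confounding adjustment, so that the example that follows it still has its context.
2. State that the visit by randomised-arm contrast, with patients analysed as assigned whatever they later receive, is the estimate of the TNF treatment effect. This also settles whether TNF treatment status means assigned or received.
3. If dose is examined, label it exploratory, confine it to the TNF arm, define the dose measure and how agents are put on one scale, and say that it does not estimate the treatment effect.

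The cost is a few lines of wording and the loss of an optional dose model. Sample size, data collection and clinical dosing are unaffected.
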